6 STUDY PROCEDURES

6.1 Schedule of Events

Activity	Phone Screen	Visit 1 Screen Visit		Visit 2 Baseline Visit	Visit 3	Visit 4	Visit 5	Phone Check 1	Visit 6/ET	Phone Check 2	Phone Check 3
		Day \geq -45		Week 1	Week 4	Week 12	Week 26	Week 39	Week 52	Week 78	Week 104
		SVa	SVb	Day 1	Day 28 + 14	Day 84 \pm 5	Day 182 \pm 14	Day 273 \pm 5	Day 364 \pm 28	Day 546 \pm 28	Day 728 \pm 28
Informed Consent		X									
Inclusion/Exclusion Review	X	X		X							
Demographics	X	X									
Medical History Review	X	X	X	X	X	X	X	X	X	X	X
Concomitant Medication Review	X	X	X	X	X	X	X	X	X	X	X
Family History Review		X									
Vital Signs, Height, and Weight ¹		X	X	X	X	X	X		X		
Physical & Neurological Exam ²		X									
Fundoscopy						X			X		
Screening Labs ³		X									
BCG Vaccination				X	X						
Injection Site Monitoring ⁴					X	X	X		X		
LP Safety Labs ⁵		X				X			X		
Blood Draw for Biomarkers			X	X	X	X	X		X		
CSF Draw for Eligibility & Biomarkers			X			X			X		
Optional MRI ⁶				X					X		
RBANS, NPI-Q, HADS				X		X	X		X		
MoCA, FAQ		X				X	X		X		
CDR				X					X		
DCT Clock				X			X		X		
Adverse Event Review		X	X	X	X	X	X	X	X	X	X

[1] Height measured at screening only. Weight measured at screening, week 26, and week 52

[2] Physical and neurological examinations will be performed at screening and at any other time if indicated per clinician investigator judgement

[3] Eligibility lab tests include CBC w/ diff, CMP, TSH, Folate, B12, HIV antibodies, serum immunoglobulins, ESR, CRP, QuantiFERON-TB Gold Test/T-spot TB test, urinalysis, PT/INR

[4] Vaccination site monitoring may include photographs of the injection site if indicated per clinician investigator judgement

[5] LP safety labs include PT/INR and CBC w/ diff

[6] Multi-sequence MRI for structural and functional measures include T1 MP-RAGE, T2 FLAIR, DWI, DTI, BOLD, ASL

An Open Label Trial to Evaluate the Effects of BCG Immunization on Biomarkers of Inflammation/Immune Response and Alzheimer's Disease in Adults with Mild Cognitive Impairment and Mild-to-Moderate Dementia due to Alzheimer's Disease

Version Date#: October 13, 2022/Version 3.3

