6.2.1.2 Screening Visits (Visit 1; Day ≥-45)

All subjects who are eligible after a telephone pre-screening will be invited to MGH CNY for Screening that will include 2 separate visits.

The first visit (SVa) will take approximately 2 hours and following procedures will be performed:

- Obtain written informed consent from subject
- Review inclusion and exclusion criteria
- Obtain medical and family history including COVID-19 history, concomitant medications and therapies
- Vital signs, height, and weight
- Obtain demographic information
- Neurocognitive and behavioral assessments: MoCA (version 8.1), CDR, FAQ
- Perform a physical, including inspection for BCG scar on either deltoid
- Perform a neurological examination
- Blood draw for screening labs

- CBC with differential
- Comprehensive metabolic panel (CMP)
- Thyroid stimulating hormone (TSH)
- B12
- Folate
- HIV antibodies
- Tuberculosis (QuantiFERON-TB Gold Test/T-Spot TB Test)
- C-Reactive Protein (CRP)
- Erythrocyte sedimentation rate (ESR)
- Serum immunoglobins (IgA, IgG, IgM)
- PT/INR
- Urinalysis
- Assess and document adverse events (AEs) after subject signs ICF

If the participant is still eligible after the first Screening visit (SVa), they will be invited to come back for a second Screening visit (SVb) which will take approximately 1 hour. The following procedures will be performed:

- Vital signs
- Blood draw for biomarkers
- Fasting CSF draw for screening (if required) and baseline biomarkers
- Assess for changes to medical history, concomitant medications and/or adverse events

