6.3.2 Physical and Neurological Examination

A physical and neurological examination will be performed at the Screening visit. The following systems will be examined: general appearance, head, eyes, ears, nose, throat, neck, chest, heart, abdomen, extremities, edema, peripheral vascular, skin and appendages, musculoskeletal, central nervous system and back. A physical and/or neurological exam may be repeated at any visit if indicated per clinician judgement.

A focused fundoscopy examination will be repeated before the second and third lumbar punctures to assess for increased intracranial pressure.

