8.2 Safety Endpoints

The primary safety endpoint will be the incidence of treatment emergent Grade II-IV adverse events.

Other safety endpoints are:

- Incidence and severity of treatment emergent adverse events (AEs)
- Clinical laboratory tests
- Vital signs
- Physical examinations
- Use of concomitant medications for treatment of AEs

All concomitant medications will be tabulated according to drug class and preferred term using the WHO dictionary. The safety data will be summarized by treatment group. Treatment AEs will be coded and graded using MedDRA grading criteria. The treatment groups will be compared with respect to occurrence of each adverse event and incidence of Grade II/IV adverse events. Withdrawal, abnormal laboratory tests, vital signs and use of concomitant medications used for treatment of AEs will be assessed to characterize the safety profile of BCG. Descriptive statistics denoting the changes from baseline to the final assessment visit with respect to key laboratory parameters and vital signs will also be provided.

Adverse events (AE) occurring after the start of study drug dosing at Baseline will be summarized descriptively. All AEs will be coded according to system organ class (SOC) and preferred term (PT) using a Medical Dictionary for Regulatory Activities (MedDRA) dictionary. Summary tables showing the number of subjects and percent within each category will be generated for each of the following types of adverse events and its relationship to study treatment (related to study treatment):

- All events
- Serious events
- Deaths
- Events leading to withdrawal
- Severe events

Treatment AEs will be coded and graded using MedDRA grading criteria. and compared with respect to occurrence of each adverse event and incidence of Grade II/IV adverse events. Total number of adverse events will be compared between groups using Fisher's exact test. Any treatment AE still present upon completion of treatment (including early discontinuation) should be monitored until resolution or until the AE is declared a chronic condition. AEs will be monitored until they become chronic or have completely resolved.

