Laboratory parameters will be summarized by visit; descriptive statistics denoting the changes from baseline to the final assessment visit with respect to key laboratory parameters and vital signs will also be provided. Frequencies of high and low values with respect to the normal range will be displayed, as will shift tables comparing each treatment visit and Baseline visit by time point.

Vital signs will be summarized across groups by visit using descriptive statistics, and at each outcome visit and at end of study. Physical examination findings and number of subjects will be summarized as the count and percentage of subjects by eCRF pre-defined categories at last visit. Change from baseline at last visit will be summarized in a shift table comparing baseline and last visit results. Concomitant medications will be summarized, drug class and preferred term.

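### Section 8.2 plans last-visit percentages and a baseline-to-last-visit shift table for physical examinations, but no full physical or neurological examination is scheduled after Screening

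*Combined protocol and SAP*

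**What the plan says.** **Analysis text.** Section 8.2 names "Physical examinations" among the other safety endpoints, below the primary one. It then commits to two summaries. The first is: "Physical examination findings and number of subjects will be summarized as the count and percentage of subjects by eCRF pre-defined categories at last visit". The second follows directly: "Change from baseline at last visit will be summarized in a shift table comparing baseline and last visit results".

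**Data collection text.** In the Schedule of Events (section 6.1), the row "Physical & Neurological Exam" carries a single mark, at the first screening visit (SVa). Its footnote reads: "Physical and neurological examinations will be performed at screening and at any other time if indicated per clinician investigator judgement". Section 6.3.2 agrees: "A physical and neurological examination will be performed at the Screening visit", and later "A physical and/or neurological exam may be repeated at any visit if indicated per clinician judgement". The screening list in section 6.2.1.2 contains the matching item: "Perform a physical, including inspection for BCG scar on either deltoid".

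Two focused examinations are scheduled after dosing, each with its own row in the Schedule: fundoscopy at Weeks 12 and 52, and injection-site monitoring at Weeks 4, 12, 26 and 52.

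**The concern.** A shift table needs two observations per participant: one before dosing and one at the end. The plan schedules only the first. Whatever fills the second column would come from examinations that a clinician decided were needed, so the participants in it are a selected subset and percentages based on them do not describe the dosed group.

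The practical risk is false reassurance. If the programmer uses the last available examination, every participant who was never re-examined appears as unchanged, although nobody looked after dosing. Section 9.1 expects axillary or cervical lymphadenopathy after vaccination, and section 6.3.2 includes the neck among the systems examined. A reader of an unshifted examination table could take it as evidence on such findings when it carries none.

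**Working it through.** The plan states no figure on this point, so there is none to reproduce. The check is a count of scheduled examinations, followed by a test of each way in which the table could be read.

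**Step 1. Scheduled full physical or neurological examinations per participant** (Schedule of Events, compared with the visit lists in sections 6.2.1 to 6.2.9):

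| Visit | Scheduled |
|---|---|
| Screening (SVa) | 1 |
| Baseline (Day 1) | 0 |
| Week 4 | 0 |
| Week 12 | 0 (fundoscopy and injection site only) |
| Week 26 | 0 (injection site only) |
| Week 52 | 0 (fundoscopy and injection site only) |
| Early Termination | 0 |
| Phone checks (Weeks 39, 78, 104) | not possible |

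The baseline value would itself have to be the Screening examination, because none is scheduled at the Baseline visit. Participants who roll over from the randomized trial do not change the count: section 6.1.1 adds no physical examination for them.

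**Step 2. Scheduled pairs.** Pairs per participant = 1 at baseline and 0 at last visit, so 0 complete pairs. For N participants the total is N × 0 = 0. This holds at N = 15 (section 8.1) and at N = 25 (section 3.1).

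**Step 3. What each reading of the table would give.** Let k be the number of participants who have an indicated examination after dosing. The documents give no value for k; it can lie anywhere from 0 to N.

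- *Last visit means Week 52.* Cells are filled only if an examination happened to be indicated at that visit. If none was, the table is empty.
- *Only re-examined participants count.* The denominator is k, chosen by clinician judgement, not N.
- *Last examination on record.* The N − k participants who were not re-examined contribute Screening against Screening and show no shift by construction. With k = 0 and N = 15, the table would read 15/15 = 100% unchanged, with no post-dose information behind it.

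**Step 4. Could the shift-table sentence concern another variable?** It names none, and its paragraph opens with vital signs. But it follows the physical-examination sentence directly and repeats that sentence's reference to the last visit, and the preceding paragraph already provides laboratory shift tables. Physical examination is the natural reading. If vital signs were meant, the shift table could be filled, because vital signs are taken at every in-person visit. The planned last-visit percentages would still fail, because that sentence names physical examination explicitly.

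**The case against.** Several points on the other side are sound and limit the finding.

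- *Some examination is scheduled after dosing.* A reader might infer that nobody is examined after Screening. That is wrong. Fundoscopy is described inside section 6.3.2, injection sites are inspected at four visits, and eyes and skin are among the systems that section 6.3.2 lists. Section 8.2 also reports by categories set in the eCRF, which is not among the documents, so it cannot be excluded that a few cells could be filled from these focused checks. They do not amount to the multi-system examination described in section 6.3.2.
- *The later examinations need not be symptom-driven.* A reader might infer that only participants with a complaint would be re-examined. The text says only that the examination must be indicated in the clinician's judgement; a laboratory value, a vital sign or an observed sign could prompt it. Selection by clinician judgement is supported; selection on symptoms is an inference.
- *The weight is modest.* A reader might infer that the primary safety objective is compromised. The primary safety endpoint in section 8.2 is Grade II-IV treatment-emergent adverse events. Section 11.3.1 counts clinically significant abnormal examination signs as adverse events, and adverse events are asked about at every visit, including by telephone. Important findings from an indicated examination therefore still reach the adverse event tables.
- *Fundoscopy is not a good replacement.* Section 6.3.2 uses it to check for raised intracranial pressure before the second and third lumbar punctures. Its Schedule row has no Screening mark, and the Early Termination list in section 6.2.9 omits it although the Visit 6/ET column marks it.

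None of this supplies the missing last-visit physical examination.

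**Conclusion.** The point holds as a mismatch between a stated analysis and the data that the design collects. Section 8.2 promises a last-visit summary of physical examinations and, on the natural reading, a shift table. The number of protocol-scheduled pairs to fill it is zero, whatever the enrolment. Followed as written, the table is empty, covers a clinician-selected subset, or shows no change by construction.

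The size is one descriptive table for an endpoint listed among the other safety endpoints. The conclusion rests on reading the shift-table sentence as referring to physical examinations, and on the eCRF categories following the full examination of section 6.3.2. It does not rest on any assumed number of indicated examinations. The text should be corrected before analysis, because the edit is cheap and the form most likely to be produced by default, last available value, is the most misleading.

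**What to change.** Reconcile section 8.2 with the Schedule of Events by rewording section 8.2:

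1. Remove the last-visit percentages and the shift table for physical examinations. If the shift-table sentence was meant for another variable, name that variable.
2. Report any physical or neurological examination done after Screening as a listing: participant, visit, reason, finding, and whether it was recorded as an adverse event.
3. Add a by-visit tabulation of injection-site findings at Weeks 4, 12, 26 and 52, graded on the toxicity scale named in section 3.3.1, with the number of participants examined at that visit as denominator. Show the two vaccination sites separately, since the second injection goes in the other arm at Week 4. For participants who roll over from the placebo arm, count weeks from their first BCG dose, as section 6.1.1 does.

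Item 3 adds real safety information. Section 8.2 does not list injection-site findings, and section 11.3.1 excludes the expected, contained site reaction from adverse events, so as the plan stands these data may appear in no planned table.

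The cost is a wording change, slightly more tabulation and the loss of one uninformative table. No visit or procedure is added. If the sponsor prefers to keep the shift table, the Schedule and section 6.3.2 would have to be changed to support it. That is a change of study procedure, not of analysis wording, and is for the sponsor to decide.

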8.3 Biofluid Biomarker, Clinical and Neuroimaging Endpoints

The change in the following assessments from Screening and/or Baseline to each post-baseline visit as described below based on the Schedule of Activities after BCG vaccination:

- Biochemical Biomarkers in Blood (Screening/Baseline, Weeks 4, 12, 26, 52) and CSF (Screening/Baseline, Weeks 12, 52) : a) Target engagement (e.g., PPD-induced PBMC cytokine release); b) Pharmacodynamic response (e.g., circulating cytokines in blood and CSF); c) AD pathophysiology (e.g., amyloid-b, tau and neurofilament light in CSF and blood); d) PBMC stimulation with AD-relevant immunogens (e.g., amyloid-b); e) Other novel biochemical biomarkers
- Clinical Neurocognitive and Behavioral Measures (Baseline, Week 12, 26 and 52): MoCA, RBANS, CDR-SB, NPI-Q, HADS, DCT Clock and FAQ
- Multi-Sequence Structural and Functional MRI (Baseline, Week 52)

Mixed-effects Model for Repeated Measures models will be used for biofluid and clinical endpoints to calculate differences at each post-baseline visit in which the biomarker is collected using baseline assessment as a covariate. Observed Case analysis will be used for differences in change of MRI measures over 52 weeks.

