3 STUDY DESIGN

3.1 Overall Study Design and Plan

This single-site, open-label trial will investigate the effects of BCG vaccination on IIR and AD biofluid biomarkers, magnetic resonance imaging (MRI) biomarkers, and neurocognitive/behavioral functioning over a one-year period in older adults with mild cognitive impairment (MCI) to mild-to-moderate dementia due to AD. This study will also gather data on tolerability and safety. Safety will continue to be followed in the second year by phone.

Up to twenty five participants meeting eligibility criteria will be enrolled. Each participant will receive two intradermal BCG vaccinations spaced 4-6 weeks apart and will be evaluated 12, 26, and 52 weeks after the initial immunization. Cerebrospinal fluid (CSF), blood, MRI (in a subset of patients), and neurocognitive/behavioral assessments will be collected at Screening (CSF, blood, and cognitive/behavioral), Week 1 (MRI and cognitive/behavioral), Week 4 (blood), Week 12 (CSF, blood, and cognitive/behavioral), Week 26 (Blood and cognitive/behavioral) and Week 52 (all) to assess biomarkers and safety. Safety measures, including updated medical history and adverse events, will be collected at Week 78 and Week 104.

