3.2 Study Objectives

The primary objectives of this study are:

1. To assess the safety and tolerability of BCG vaccination in older adults with MCI and mild to moderate dementia due to AD.
2. To investigate the potential of BCG vaccination as an immunomodulatory and CNS-protective agent for AD by evaluating changes from baseline in IIR and AD biomarkers in blood and CSF following BCG vaccination;
3. To measure changes in neurocognitive/behavioral functioning following BCG vaccination (MoCA, RBANS, CDR-SB, NPI-Q, HADS, FAQ, DCT Clock).

The secondary objective of the study is:

1. To measure changes in structural and functional neuroimaging following BCG vaccination;

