3.3.2 CSF and Blood Biomarker Outcomes

CSF and blood will be collected at Screening, Week 4 (blood only), Week 12, Week 26 (blood only), and Week 52 visits to examine biochemical biomarkers of:

1. Target engagement: BCG, purified protein derivative (PPD) and / or mycobacterium tuberculosis (heat-killed, mTB) – induced cytokine response in peripheral blood cells will be used to evaluate for BCG vaccine-induced immunity.
2. Pharmacodynamic response: a) Circulating cytokines and other related blood- and CSF-based IIR biomarkers relating to innate and adaptive immune responses; b) Epigenetic changes in peripheral blood cells and / or CSF- derived cell populations as indicators that BCG can lead to long term changes in peripheral and central nervous system immune cells.
3. AD pathophysiology: Amyloid- β 42/40, phospho-tau, total tau and / or neurofilament light protein biomarkers (ATN) and other exploratory AD-relevant synaptic and IIR biomarkers may be compared within subjects over time and between subjects and groups.
4. BCG effects on the interactions of IIR and amyloid: We will perform PBMC stimulation with A β 42 and positive-control antigens (e.g. lipopolysaccharide) and measure the molecular response in the supernatant at multiple timepoints after BCG /treatment. A β 42 has immunostimulatory / inflammatory effects that increase with AD progression and may be modulated by an immune-provoking stimulus such as BCG.
5. Additional related Alzheimer's Disease and immune measures in plasma, CSF, and their cell populations at the transcriptional, protein, or epigenetic levels.

We have several robust platforms in the [name] lab (which serves as the Biomarker Core of the Massachusetts Alzheimer's Disease Research Center) to conduct these assays, including highly validated Euroimmun assays, Fujirebio Lumipulse assays, Meso Scale Discovery with plates run on a new Tecan EV0200 multi-functional robotic liquid handling platform, and Quanterix SR-X for ultrasensitive Simoa assays. We have exhaustively validated many assays specifically for use in short-term clinical trials⁴⁹, and all assays that we propose demonstrate good precision and biotemporal stability. Change in a composite score from Baseline will be used as an outcome of response to BCG.

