6.1.1 RCT roll over participant schedule

Participants enrolled in the original randomized-controlled BCG trial will be invited to roll into the open-label trial at their scheduled Visit 3 using a Consent addendum. After unblinding the randomization schedule, participants will be told which study vaccine they received at their Baseline Visit.

If at Baseline, the participant received BCG, they will proceed in the study along the same schedule outlined in the Schedule of Events, receiving their second BCG vaccine at Visit 3/Day 28.

If at Baseline, the participant received placebo, their Day 28 visit will become their new Day 1 visit. At this Day 1 visit we will collect vitals and administer the first BCG vaccine. No additional blood or CSF will be collected, nor will any cognitive testing be performed. The participant will receive their second BCG vaccine approximately 1 month after the first BCG vaccine, and continue on the Schedule of Events outlined after the Day 1 visit in Section 6.1. The total time in the study will be extended by 1 month for participants originally assigned to the placebo arm of the randomized controlled trial.

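### Section 8.3 puts baseline in as a covariate although the target is one-arm change from baseline; read at the observed mean baseline, the standard error is too small

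*Combined protocol and SAP*

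**What the plan says.** Section 3.1 describes a single-site, open-label trial: "Each participant will receive two intradermal BCG vaccinations spaced 4-6 weeks apart". There is no concurrent control. Primary objective 2 in section 3.2 is pursued by "evaluating changes from baseline in IIR and AD biomarkers in blood and CSF following BCG vaccination", and objective 3 concerns changes in cognition and behaviour.

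Section 8.3 defines the endpoints as "The change in the following assessments from Screening and/or Baseline to each post-baseline visit". It then gives one model sentence for biofluid and clinical endpoints: a mixed model for repeated measures is used "to calculate differences at each post-baseline visit in which the biomarker is collected using baseline assessment as a covariate". It does not say what is differenced, whether the response is the raw value or the change, at which baseline value the visit means are evaluated, or how the standard error is obtained.

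Two other places carry two-arm language or history. Section 8.2 says "Total number of adverse events will be compared between groups using" Fisher's exact test, although there is one arm. Section 6.1.1 says "Participants enrolled in the original randomized-controlled BCG trial will be invited to roll into the open-label trial".

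**The concern.** In a two-arm comparison, a baseline covariate sharpens the difference between arms, and uncertainty in the overall baseline mean largely cancels. In a one-arm mean change it does not cancel, because the baseline mean is half of the quantity being estimated. A model that conditions on baseline treats that mean as fixed. The covariate wording may have come from the earlier randomized trial. That is an inference, since the earlier protocol is not available.

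This is the only model stated for primary objectives 2 and 3. With about 15 participants and no control, intervals for within-person change are the main inferential output. If they are too narrow, a biomarker or cognitive shift will look better established than it is. Using change as the response does not help: with baseline still in the model, the standard error is the same.

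**Working it through.** **Inputs.** From the documents: one arm (3.1); n of about 15, set by feasibility (8.1); 12 expected completers (4.2); a cap of 25 (3.1). Not in the documents, so assumed: pre/post correlation r from 0.3 to 0.9, two-sided 5%, normal data, no true change. The plan states no alpha, power, SD or effect size, so there is no figure to reproduce first.

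**Formula.** Let s0 and s1 be the pre and post SDs, and b = r × s1/s0 the slope of post on baseline. With complete data, the adjusted visit mean at the observed mean baseline, minus that baseline mean, equals the sample mean change. The variances are:

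- population mean change: [s1²(1 − r²) + s0²(1 − b)²]/n
- covariate model at the observed mean baseline: s1²(1 − r²)/n

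The omitted term, (1 − b)² × Var(baseline mean), is never negative and vanishes only when b = 1. With s0 = s1 the variance ratio is (1 − r²)/[2(1 − r)] = (1 + r)/2.

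**Example.** n = 15, r = 0.5, SD = 1. The correct SE is √(2 × 0.5/15) = 0.258; the model SE is √(0.75/15) = 0.224. The ratio is 0.866, which is √(1.5/2).

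**Error rate and coverage, equal SDs** (simulation, 200,000 trials per cell; repeat runs differ by up to about 0.2 points):

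| r | SE ratio | Type I, n = 12 | Type I, n = 15 | Coverage, n = 15 |
|---|---|---|---|---|
| 0.3 | 0.81 | 10.3% | 10.4% | 89.6% |
| 0.5 | 0.87 | 8.2% | 8.4% | 91.6% |
| 0.8 | 0.95 | 6.1% | 6.1% | 93.9% |
| 0.9 | 0.97 | 5.5% | 5.5% | 94.5% |

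Paired change gives about 5% in every cell. At n = 25 the covariate model gives 10.9%, 8.6%, 6.2% and 5.5%, so enrolling to the cap does not cure it.

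**By visit.** Assume correlation decays by 0.8 per assessment, so r with baseline is 0.80, 0.64, 0.51 and 0.41. At n = 15, Weeks 4, 12, 26 and 52 give 6.2%, 7.2%, 8.1% and 9.2% with a baseline slope for each visit. With one slope common to all visits they give 5.7%, 7.0%, 7.6% and 8.3%.

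**If the SD changes after BCG** (n = 15; r = 0.3, 0.5, 0.8):

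| Post/pre SD ratio | Type I error |
|---|---|
| 0.8 | 15.0%, 12.6%, 10.7% |
| 1.25 | 7.9%, 6.2%, 5.0% |
| 1.5 | 6.5%, 5.3%, 5.5% |
| 2 | 5.5%, 5.0%, 7.6% |

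The 5.0% entries are where b is at or near 1. For example, 0.8 × 1.25 = 1.

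**A pre-set baseline value is not a remedy.** Evaluating at a fixed x0 biases the change by (b − 1)(x0 − μ), where μ is the true baseline mean. At n = 15 and r = 0.3, 0.5, 0.8, a value 0.25 SD off μ gives 9.4%, 7.7% and 5.9%; 0.5 SD off gives 20.9%, 14.8% and 8.2%.

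**Test of the replacement.** With complete data, an unstructured model with baseline as a response reduces to the paired t test: 4.9–5.1% at every visit. With an assumed 20% random dropout, Kenward-Roger standard errors and a paired fallback (2,000 trials per cell, Monte Carlo error about 0.5 points), it gives 4.0–5.4% at n = 15 and 4.6–6.0% at n = 12. Compound symmetry fitted to the decaying-correlation data gives 1.3%, 5.8%, 10.0% and 13.4% at the four visits (n = 15), so it is not a safe fallback.

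**The case against.** The strongest reply is that the plan does not commit this error. Section 8.3 never says where visit means are evaluated or what contrast is formed, and the conditional standard error is correct for the change at the baselines actually sampled. The point estimate is unbiased with complete data. No alpha or success rule depends on the result. The correlation is unknown, and section 3.3.2 claims biotemporal stability for the assays, which points toward higher r and a small effect. Section 3.3.2 also allows comparisons between groups, and the population runs from MCI to moderate dementia. Finally, an unstructured model with 15 covariance parameters for blood is heavy for about 12 completers.

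Much of this stands as a limit on size. The stability claim carries no figure, but if r is near 0.9 with equal SDs the loss is half a point of coverage. The Week 52 result depends on the assumed decay. Three things do not fall. The stated target is within-person change, and the undefined groups in section 3.3.2 do not alter that. The usual output from the stated model would be read as mean change in this population, for which the interval is too narrow. The model also gains nothing in exchange, because there is no arm difference to sharpen. The concern about model size is met by naming paired change as the fallback.

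**Conclusion.** The concern holds, as a conditional one. If the visit means are evaluated at the observed mean baseline and read as population mean change, the standard error is too small unless b = 1. With equal SDs the shortfall is about 19% at r = 0.3, 13% at 0.5, 5% at 0.8 and 2.5% at 0.9. Across the SD ratios tried, nominal 5% error runs from 5.0% to 15.0%.

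The size rests on assumed correlations and SD ratios. The default evaluation point is likely but unstated. The harm is to interval coverage, not to a declared test. It should be fixed before analysis, because the stated method does not match the stated target. Confidence is medium, because the plan leaves the evaluation point open.

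**What to change.** In section 8.3, replace the covariate wording with:

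> Pre-vaccination values enter the repeated-measures model as responses. Visit is categorical. The estimate is the contrast of each post-BCG visit with the pre-BCG value, using an unstructured covariance with Kenward-Roger standard errors. If that model does not converge, each post-BCG visit is compared with baseline by a paired-change analysis (mean change, its SD and t interval) in participants with both values. Compound symmetry is not used as the fallback.

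The cost is wording, plus wider intervals: 1/0.81, 1/0.87, 1/0.95 and 1/0.97, or about 24%, 15%, 5% and 3% wider at r = 0.3, 0.5, 0.8 and 0.9 with equal SDs (percentages from the unrounded ratios). The covariance has k(k + 1)/2 parameters: 15 for blood (5 assessments), 10 for measures taken four times such as RBANS and MoCA, 6 for CSF and DCT Clock, 3 for CDR. In the 20% dropout test with 5 assessments, the fit failed to converge in 0.15–0.35% of trials at n = 15 and 1.5–2.0% at n = 12. That test covered random dropout only, and the paired fallback loses anyone without both values.

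A minor clarification can go in with the same edit: say which pre-BCG blood draw is baseline. The schedule in section 6.1 has biomarker draws at both SVb and Day 1, while section 3.3.2 says "CSF and blood will be collected at Screening, Week 4 (blood only), Week 12, Week 26 (blood only), and Week 52 visits". Also name the baseline for former-placebo rollovers, for whom section 6.1.1 says of the new Day 1: "No additional blood or CSF will be collected, nor will any cognitive testing be performed".
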